#### 5.2. Secondary outcomes

- 1. Proportion of participants that achieves an 8-point improvement in ISI
- 2. Pain intensity measured using a numerical rating scale from 0 to 10.
- 3. Health-related quality of life measured by the EuroQol 5-Dimension (EQ-5D).
- 4. Mental distress using the Hopkin symptoms checklist-5.
- 5. Work ability using the Work Ability Index (WAI).
- 6. Self-reported use of sleep and pain medication

# **5.2.1.** Analysis of secondary outcomes

For continuous secondary outcomes assessed at multiple follow-up timepoints, similar linear mixed effects models (LMMs) as for the primary outcome measure (ISI) will be used. For binary secondary outcomes we will use a mixed logistic regression model to estimate the odds ratio (OR).

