#### 2.8.1. Timing of outcome assessments

The trial has five measurement points (Table 1): Baseline measurements prior to the randomization and the start of the intervention, and follow-up at 6 weeks, and 3-, 6-, and 12 months after start of intervention. Primary outcome is ISI at 3 months follow up.

**Table 1**: Assessed variables with respective questionnaires and schedule of assessment.

Name of variable	Measurement points					
	Baseline	6-weeks	3-months (Primary endpoint)	6-months	12-months	
Demographics						
Sex, age, education, economy, work schedules, shift work, living status and number of children under and/or over six years old living at home	X					
Lifestyle and health-related parameters						
Leisure time physical activity	Х		Х			
Alcohol consumption and use of drugs	Х					
Height and body weight	X					
Self-reported and prescribed sleep and pain medications	X	Х	Х	Х	Х	
		_ ^	^	Λ	Λ	
Health literacy  Work ability assessed by the Work Ability Index (de Zwart et al., 2002; El Fassi et al., 2013)	X		X		Х	
Sleep and circadian rhythms						
Insomnia severity assessed using the Insomnia severity index (Morin et al., 2011)	Х	Х	Х	Х	х	
Sleep diary (intervention only). Collected by app	Х	Х				
Beliefs and attitudes about sleep assessed using the Pain- Related Beliefs and Attitudes about Sleep (Afolalu et al., 2016)	Х					
Stress-induced sleep reactivity assessed using Ford Insomnia Response to Stress (Drake et al., 2004)	Х					
Chronotype assessed using the reduced Horne-Ostberg- Morningness-Eveningness Questionnaire (Chelminski et al., 2000)	Х					
Duration of sleep problems	Х					
Previous treatment of insomnia	Χ					
Other sleep therapy/sleep advice during the project period	Х	Х	Х	Х	Х	
Sleep self-efficacy	Χ	Х	Х			
Sleep-talking, sleepwalking, possible restless legs/sleep apnea	Х					
Pain						
Pain duration	Х					
Pain intensity last week assessed using the Örebro Musculoskeletal Pain Screening Questionnaire short form (Linton et al., 2011)	Х	X	Х	Х	X	
Patients' expectations about the treatment	X					
Fear avoidance assessed using the Örebro Musculoskeletal Pain Screening Questionnaire short form	Х					
Pain sites assessed using the Standardised Nordic questionnaires (Kuorinka et al., 1987)	Х					
Musculoskeletal health assessed using the Musculoskeletal health questionnaire (Hill et al., 2016)	Х	Х	X	Х	Х	
Pain self-efficacy assessed using the Pain Self-Efficacy Questionnaire-2 items (Nicholas et al., 2015)	Х					

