## 3. Statistical principles

# 3.1. Confidence intervals and p-values

Estimates will be presented as mean differences or odds ratios with 95% confidence intervals. All p-values will be two-sided, and the significance level will be set to 0.05. No formal adjustment for multiple testing for secondary endpoints is made, but the issue of multiple testing will be kept in mind when interpreting results.

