# 5.1.2. Analysis of primary outcome

In the primary analysis we will use linear mixed model analysis to estimate mean difference in ISI between the two groups at 3 and 6 months of follow-up, with 3 months as the primary endpoint for the outcome measurement. The model will include participant ID as a random effect. Time, group, and time-group interaction, will be used as fixed effects. Group means will be constrained to be equal at baseline due to the randomization (Coffman, Edelman & Woolson, 2016). Following evidence-based recommendations (Kahan & Morris, 2012; Kahan et. al., 2014), we will adjust for potentially important predictors of the outcome including age (years), sex (male vs female) and mean pain intensity level (0-10 scale). Unadjusted analysis will also be performed. The model assumptions for mixed models will be checked.

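### Carried over unchanged to pain intensity, the primary model uses baseline pain as both outcome row and covariate, so that outcome's adjusted standard error is too small

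*SAP*

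**What the plan says.** SAP section 5.1.2 defines one linear mixed model for ISI.

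- Random part: "The model will include participant ID as a random effect". No other residual structure and no robust standard error is named.
- Baseline: "Group means will be constrained to be equal at baseline due to the randomization". A model with this constraint has the baseline measurement in the response, as a row of its own.
- Covariates: "age (years), sex (male vs female) and mean pain intensity level (0-10 scale"). The time of the pain measurement is not given. An unadjusted analysis is planned as well.

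Section 5.2 lists as its second secondary outcome "Pain intensity measured using a numerical rating scale from 0 to 10". Section 5.2.1 carries the model over: "similar linear mixed effects models (LMMs) as for the primary outcome measure (ISI) will be used". It makes no exception for pain.

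Table 1 in section 2.8.1 has a single pain-intensity entry ("Pain intensity last week assessed using the Örebro" short form), scheduled at baseline and at every follow-up. Covariate and outcome therefore appear to be the same item.

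On the error rate, section 3.1 says: "All p-values will be two-sided, and the significance level will be set to 0.05".

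**The concern.** A constrained-baseline model already uses baseline pain, through its correlation with the follow-up values. Adding baseline pain as a covariate enters it a second time, and in the baseline row the covariate equals the response.

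Two things follow. The common slope is a compromise between 1 (baseline row) and the true regression of follow-up on baseline, so chance baseline imbalance is over-corrected. The baseline residuals become very small, and a random-intercept model pools them with the follow-up residuals into one variance. The variance credited to the follow-up contrast is then too low.

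At stake are the confidence interval and p-value of the adjusted pain analysis. Pain intensity is named in the secondary objectives, and section 3.1 plans no multiplicity adjustment for secondary endpoints, so nothing else in the plan offsets an inflated error rate.

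**Working it through.** **Inputs from the SAP.** Two-sided level 0.05 (3.1); 188 participants, 94 per arm, and 30% dropout at 3 months (2.4); fallback of 140 (2.7). Rows are baseline, 3 and 6 months (5.1.2), or these plus 6 weeks (1.3.2).

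**Assumptions.** The SAP gives neither an SD nor a within-person correlation for pain. SD 2 is used; it cancels from the error rate. Correlation ρ is taken as 0.3, 0.5 and 0.7, equal between all visits unless stated.

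**Step 1: a case that can be checked by hand.** T = 3 rows, ρ = 0.5, no dropout, variances in units of SD².

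- Fitted slope: g = (1 + (T−1)ρ)/T = (1 + 2 × 0.5)/3 = 0.667. The correct slope is 0.50.
- Residual variance, baseline row: (1−g)² = 0.111. Each follow-up row: 1 − 2gρ + g² = 0.778. Average: (0.111 + 2 × 0.778)/3 = 0.556.
- Residual covariance, baseline with follow-up: (1−g)(ρ−g) = −0.056. Between follow-ups: ρ − 2gρ + g² = 0.278. Average over the three pairs: (2 × (−0.056) + 0.278)/3 = 0.056.
- Intraclass correlation seen by the model: λ = 0.056/0.556 = 0.10.
- The estimate is the follow-up difference minus k times the baseline difference, with k = g + λ(1−g) = 0.667 + 0.10 × 0.333 = 0.70.
- True variance factor: 1 − 2kρ + k² = 1 − 0.70 + 0.49 = 0.79. Model variance factor: 0.556 × (1 − 0.10²) = 0.55.
- With 2 × 2²/94 = 0.0851: true SE = √(0.0851 × 0.79) = 0.259; model SE = √(0.0851 × 0.55) = 0.216; ratio 0.834.
- Type I error: 2Φ(−1.96 × 0.834) = 0.102.

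Simulation of this case gave slope 0.67, true SE 0.258, model SE 0.216 and type I error 0.104.

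**Step 2: the nominal level is reproduced.** Without the pain covariate the same case gives √(0.0851 × (1 − 0.5²)) = 0.253. The simulation gave model SE 0.252, true SE 0.251 and type I error 0.050.

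**Step 3: range.** 2000 null trials per setting (Monte Carlo SE near the nominal level √(0.05 × 0.95/2000) = 0.005), REML, Wald test of the 3-month difference, N = 188, baseline pain as both row and covariate:

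| Rows | Dropout | Type I error at ρ = 0.3 / 0.5 / 0.7 | Model SE ÷ true SE |
|---|---|---|---|
| baseline, 3, 6 months | 0% | 0.097 / 0.104 / 0.113 | 0.86 / 0.84 / 0.82 |
| baseline, 3, 6 months | 30% | 0.136 / 0.142 / 0.155 | 0.78 / 0.75 / 0.74 |
| with 6 weeks | 0% | 0.077 / 0.087 / 0.093 | 0.90 / 0.88 / 0.85 |
| with 6 weeks | 30% | 0.095 / 0.099 / 0.110 | 0.85 / 0.83 / 0.81 |

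With N = 140, ρ = 0.5 and 30% dropout: 0.129 without and 0.103 with the 6-week row. With correlation decaying over time and 30% dropout (N = 188): 0.114 and 0.116.

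**Step 4: over-correction.** In step 1 each point of baseline imbalance moves the estimate by 0.70 − 0.50 = 0.20 points too far. The imbalance has SD √0.0851 = 0.29, so a typical shift is 0.20 × 0.29 = 0.06 points, with either sign.

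**Step 5: remedies, equal correlations, N = 188.** Pain covariate dropped: 0.044-0.058. Follow-up rows only, with baseline pain as covariate: 0.044-0.057. In both, model SE ÷ true SE is 0.97-1.01.

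**The case against.** The strongest reply is that section 5.2.1 promises similar models, not identical ones. The covariates in 5.1.2 were chosen as likely predictors of the outcome, and a statistician who supervises the secondary analyses could drop pain when pain is the outcome. That stands in part: the wording permits the correct analysis. It does not require it, and the SAP nowhere states the exception. A reader might infer that the plan commits itself to the faulty model; the text supports only that the fault follows if the model is carried over unchanged.

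Second, an unadjusted analysis is planned, has no pain covariate and keeps its error rate. Model assumptions are also to be checked, and residuals by visit could reveal the collapse at baseline. Both points stand. However, the SAP does not say which analysis leads for pain if the two disagree.

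Third, the effect is small in absolute terms. With the 6-week row, 30% dropout and ρ = 0.5, the SEs are 0.260 and 0.315, so the half-width of the interval is short by 1.96 × 0.055 = 0.11 points on a 0-10 scale. One unranked secondary outcome is concerned. That limits the weight of the point but does not remove it.

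A reader might also infer that 5.1.2 allows a post-randomisation pain value as covariate, because pain is measured at every visit. That reading is strained: pain stands beside age and sex as a predictor, which points to a baseline value. The missing word is a minor wording point.

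**Conclusion.** The concern holds, conditionally. If the model of 5.1.2 is applied to pain intensity without an exception, the adjusted analysis of that outcome has a standard error about 10-26% too small. Its two-sided type I error is then about 8-15% (7.7-15.5% over the settings tried) instead of 5%. The direction was the same in every setting. The size rests on assumed correlations of 0.3-0.7, dropout of 0-30% and the choice of rows; it is largest when the 6-week row is left out and dropout is 30%.

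Two stronger conclusions do not follow. The pain estimate is not biased on average: the excess adjustment matters only given a chance baseline imbalance. The primary result is not touched either, since the double use arises only where the covariate is also the outcome. ISI, the other secondary outcomes and the unadjusted pain analysis are free of it. This is a point to correct before analysis, not one that threatens the trial's main conclusion.

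**What to change.** Add one sentence to 5.2.1, choosing one of two forms:

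- for pain intensity, the pain covariate is omitted, age and sex are kept, and the constrained-baseline model accounts for baseline pain; or
- for pain intensity, only follow-up rows are modelled, with baseline pain, age and sex as covariates.

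The first stays closer to the model already specified. In 5.1.2, write *baseline* before the pain-intensity covariate.

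The cost is one sentence and one word, with no new data and no change to the sample size or to the ISI model beyond that clarification. The change should be made before allocation is revealed, in line with the aim in section 1.1.

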# 1.3.2. Secondary objectives

- I. Evaluate the effectiveness of dCBT-I on physical function, pain intensity, health-related quality of life, mental distress, work ability, and self-reported use of sleep and pain medication at 6 weeks, 3 months follow-up (primary outcome) and 6 months follow-up.
- II. Examine the difference in the proportion of participants in the intervention and the control group that achieves a clinically relevant (i.e., 8-point Insomnia Severity Index [ISI] decrease) improvement in insomnia severity at 6 weeks, 3 months follow-up (primary outcome) and 6 months follow-up.

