#### 5.3. Missing data

We will use the linear mixed model analyses, which provides unbiased effect estimates under the assumption that the outcome data is missing at random. In a sensitivity analysis, missing values will be imputed using a multivariate normal approach with 20 imputed data sets.

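### As written, nothing brings baseline ISI into the model for the 8-point ISI responder outcome, because the primary model's way of using it cannot carry over

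*SAP*

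**What the plan says.** The responder outcome heads the list in SAP 5.2: "Proportion of participants that achieves an 8-point improvement in ISI". It is the whole of secondary objective II in SAP 1.3.2, which is to "Examine the difference in the proportion of participants in the intervention and the control group that achieves a clinically relevant" "improvement in insomnia severity at 6 weeks, 3 months follow-up (primary outcome) and 6 months follow-up" (an ISI fall of 8 points is given there as the criterion).

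Its analysis is one sentence in SAP 5.2.1: "For binary secondary outcomes we will use a mixed logistic regression model to estimate the odds ratio (OR"). The sentence before it reads "For continuous secondary outcomes assessed at multiple follow-up timepoints, similar linear mixed effects models (LMMs) as for the primary outcome measure (ISI) will be used", so the link to the primary model is made for continuous outcomes only.

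In the primary model (SAP 5.1.2), baseline ISI enters through one device: "Group means will be constrained to be equal at baseline due to the randomization". The adjustment set is described as "potentially important predictors of the outcome including age (years), sex (male vs female) and mean pain intensity level (0-10 scale"). Baseline ISI is not named there and does not need to be, because it is already an outcome row.

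On missing data, SAP 5.3 states: "We will use the linear mixed model analyses, which provides unbiased effect estimates under the assumption that the outcome data is missing at random". It adds a sensitivity analysis by multivariate normal imputation with 20 data sets, without saying which outcomes or variables it covers.

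**The concern.** An absolute 8-point fall on a 0 to 28 scale can depend on where the participant starts. Someone entering at 12 must reach 4 or lower, while someone entering at 24 need only reach 16. The starting score is thus an obvious candidate predictor of response, and SAP 5.1.2 itself commits to adjusting for such predictors.

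The primary model handles this without listing baseline ISI as a covariate. The responder model cannot do it the same way. Change from baseline is zero for everyone at baseline, so a baseline row would carry no information.

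Two things are at stake: some power, and the handling of dropout. The sample size section allows for 30% dropout. If those still answering differ between arms in starting severity, a responder model without baseline ISI does not condition on that difference, whereas the primary model does.

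**Working it through.** **Inputs from the SAP.** ISI range 0 to 28 (5.1.1). Target difference 3 points, 72 per arm for 90% power, 94 per arm recruited, 30% dropout (2.4). Fallback 70 per arm (2.7). Completers per arm: 94 × 0.7 = 65.8, about 66; fallback 70 × 0.7 = 49. The SAP gives no figure for the responder analysis, so there is none to reproduce.

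**Inputs assumed.** The SAP gives no SD. Back-solving 72 = 2(1.960 + 1.282)²σ²/3² gives σ ≈ 5.55, used as the follow-up SD. Also assumed: baseline mean 17 and SD 4, a control fall of 3 points, and a baseline to follow-up correlation ρ of 0.3 to 0.7.

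**Step 1. Does response depend on the starting score?** Control follow-up at baseline b has mean 14 + (5.55ρ/4)(b − 17) and SD 5.55√(1 − ρ²). With integer scores, P(response) = Φ[(b − 8 + 0.5 − mean)/SD].

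| ρ | Slope 5.55ρ/4 | SD | b = 12: mean, P | b = 24: mean, P |
|---|---|---|---|---|
| 0.3 | 0.416 | 5.29 | 11.92, Φ(−1.40) = 8% | 16.91, Φ(−0.08) = 47% |
| 0.5 | 0.694 | 4.81 | 10.53, Φ(−1.25) = 10% | 18.86, Φ(−0.49) = 31% |
| 0.7 | 0.971 | 3.96 | 9.14, Φ(−1.17) = 12% | 20.80, Φ(−1.08) = 14% |

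Simulation gives the same picture (8% vs 47%, 10% vs 31%, 12% vs 13%). At ρ = 0.7 the slope is close to 1, so the expected change is nearly the same at every starting score and the dependence vanishes.

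**Step 2. Power.** Logistic regression at 3 months, 2,000 simulated trials per scenario, without and then with baseline ISI:

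| ρ | 66 per arm | 49 per arm |
|---|---|---|
| 0.3 | 62% → 66% | 49% → 51% |
| 0.5 | 73% → 74% | 58% → 59% |
| 0.7 | 87% → 87% | 75% → 75% |

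The standard error of the log OR does not fall. At 66 per arm and ρ = 0.3 it goes from 0.393 to 0.421, while the log OR goes from 0.88 to 0.99. The ratio rises from 0.88/0.393 = 2.24 to 0.99/0.421 = 2.35.

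**Step 3. Dropout related to baseline ISI.** Random-intercept logistic model over three visits, large sample (30,000), about 30% missing. Dropouts have no follow-up visit at all in these runs, so other visits cannot help them. Differences in 3-month response proportions, in percentage points, are obtained by subtracting the arm proportions:

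| ρ and dropout pattern | True | Without baseline ISI | With |
|---|---|---|---|
| 0.4, same in both arms | 36.1 − 17.5 = 18.6 | 33.3 − 15.1 = 18.2 | 36.4 − 17.0 = 19.4 |
| 0.4, severe drop out, dCBT-I arm only | 18.6 | 33.4 − 17.4 = 16.0 | 36.4 − 17.3 = 19.1 |
| 0.4, mild drop out, dCBT-I arm only | 18.6 | 38.3 − 17.6 = 20.7 | 35.5 − 17.6 = 17.9 |
| 0.4, opposite by arm | 18.6 | 33.8 − 18.8 = 15.0 | 36.2 − 17.2 = 19.0 |
| 0.6, opposite by arm | 32.9 − 13.3 = 19.6 | 32.1 − 14.1 = 18.0 | 33.1 − 13.5 = 19.6 |

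Across the arm-specific patterns the marginal OR ranges from 2.20 to 2.90 without baseline ISI and from 2.58 to 2.74 with it (true 2.66) at ρ = 0.4. At ρ = 0.6 it ranges from 2.89 to 3.37 and from 3.16 to 3.20 (true 3.20).

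A single-visit check used baseline mean 17.4 and SD 3.5, with dropout in opposite directions by arm at 0.1 to 0.2 log-odds per ISI point. It gave a bias of 2 to 5 points at ρ = 0.3 and 1 to 2 points at ρ = 0.5. Adding baseline ISI brought the estimate within 0.2 point of the truth.

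**The case against.** The strongest reply is that SAP 5.2.1 is silent, not wrong. It names no covariates for binary outcomes, not even time or group, and the list in 5.1.2 is introduced as non-exhaustive. A reader might infer that the plan has chosen to exclude baseline ISI. The text does not support that; the defect is under-specification. What stands against the reply is that completing the model from what 5.1.2 names still leaves baseline ISI out.

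A reader might also infer a loss of precision in the usual sense. Step 2 shows otherwise: the standard error of the log OR rises with adjustment, and the gain is a small one in power.

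Nor is the comparison biased merely because a baseline predictor is omitted from a randomised comparison. The bias requires baseline-related dropout that differs by arm, and the SAP gives no sign of such a pattern. Where the relation is the same in both arms, the contrast barely moves, although both proportions shift by 2 to 3 points. Even an adverse bias is smaller than the sampling error: with assumed responses of 17% and 37%, √[(0.17 × 0.83 + 0.37 × 0.63)/66] = 7.5 percentage points.

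Finally, dropout protection is not wholly lost. The mixed logistic model uses the other visits of a participant who misses one. The imputation in 5.3 could restore the baseline information if it covers this outcome and includes baseline ISI, but neither is stated.

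**Conclusion.** The point holds as a gap in specification with modest consequences. Nothing in the SAP as written brings baseline ISI into the responder model, and the primary model's device cannot be borrowed.

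Under the assumed inputs the cost is about 0 to 4 points of power at 66 per arm. If baseline-related dropout differs between arms, the bias can go in either direction, up to about 5 percentage points at a correlation of 0.3 and close to none at 0.7. A wider spread of baseline scores or a stronger link with dropout would enlarge it; participants' other visits and a properly specified imputation would reduce it. The correlation, the baseline distribution and the dropout pattern are all assumptions, since the SAP gives none of them.

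The primary continuous ISI analysis is unaffected. The change is still worth making before unblinding, because this outcome carries the trial's statement on clinically relevant improvement.

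**What to change.** Add to SAP 5.2.1, for example: *The 8-point ISI responder model uses the follow-up visits only (no baseline row), with time, group and time-by-group as fixed effects and participant as a random effect, adjusted for continuous baseline ISI, age, sex and baseline pain intensity. Standardised response proportions by arm and their difference, with 95% confidence intervals, are reported beside the OR.*

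Add to 5.3: *For the responder outcome, the ISI score is imputed, with baseline ISI in the imputation model, and responder status is derived afterwards.*

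The cost is a few lines of text and no new data, since ISI is scheduled for collection at baseline. The one downside is that the OR becomes conditional on baseline ISI. It is already conditional on the participant effect: with dropout unrelated to anything and ρ = 0.4, the model without baseline ISI gave a conditional OR of 4.56 against a marginal 2.67. The standardised proportions deal with both, and they answer objective II directly, since it asks for a difference in proportions.

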#### 2.2. Randomization and treatment assignment

Participants will be block randomized in a 1:1 ratio to either the intervention group (usual treatments provided by a physiotherapist + dCBT-I) or the control group (usual treatments provided by a physiotherapist). Randomization will be performed by a researcher using a secure digital platform for multicentre clinical studies, eForsk. In eForsk, a third-party user from the Section for Research at St Olav's hospital will set up the randomization procedure, blinded to the project group. [name] will conduct the allocation.

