#### 2.4. Determination of sample size

Previous studies show that the intervention effect in ISI from baseline to after intervention was 2.8-4.7 points in the intervention group compared to the control group (Vedaa et al., 2020; Wiklund et al., 2022). We therefore estimated that a sample size of 144 (72 in each group) was necessary to detect a 3-point difference with 90% power and a 2-sided alpha level of .05. Previous RCTs of dCBT-I report sample attrition rates between 12% and 50%(Christensen et al., 2016; Vedaa et al., 2020). To allow for a 30% dropout rate a 3-months follow-up, we aim to include 188 participants (94 participants in each arm) to answer our primary aim.

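### Secondary objective II asks for a difference in responder proportions, but the only planned estimate is an odds ratio from a mixed logistic model, which does not give that difference

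*SAP*

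**What the plan says.** SAP section 1.3.2 words objective II as follows: "Examine the difference in the proportion of participants in the intervention and the control group that achieves a clinically relevant" improvement, defined as an 8-point ISI decrease, at 6 weeks, 3 months and 6 months. Section 5.2 lists it first among six secondary outcomes: "Proportion of participants that achieves an 8-point improvement in ISI".

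The analysis is in section 5.2.1: "For binary secondary outcomes we will use a mixed logistic regression model to estimate the odds ratio (OR"). Section 3.1 sets the reporting scale for the whole plan: "Estimates will be presented as mean differences or odds ratios with 95% confidence intervals". Section 5.2.1 does not say which random effect the logistic model has. The only one named in the SAP is in section 5.1.2, for the primary model: "The model will include participant ID as a random effect".

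The abbreviation list contains the risk ratio, but no analysis uses it. The SAP mentions no risk difference, standardised proportion or population-averaged model.

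**The concern.** The objective is phrased on the scale of proportions and the estimate is on the odds scale. With a participant-level random intercept there is a further step between them. The odds ratio compares the odds of response for the same underlying participant under the two treatments, not the odds in the two arms as groups. One such odds ratio is compatible with many differences in proportions, depending on the control rate and on how strongly responses correlate within a participant.

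Two things are at stake. The quantity named in the objective has no pre-specified estimate or interval, so any difference reported later would have been chosen without a plan. And a reader who takes the conditional odds ratio for a population one would infer too large an absolute benefit.

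**Working it through.** **Plan's own figure.** There is none to reproduce. The SAP gives no responder rate, odds ratio or power for this outcome. Its sample size (section 2.4) concerns mean ISI: it "was necessary to detect a 3-point difference with 90% power and a 2-sided alpha level of .05".

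**Inputs.** From the SAP: a binary outcome (8-point ISI decrease), a mixed logistic model, and odds ratios as the reporting scale. Assumed, because the SAP does not give them: responder rates of 20% (control) and 40% (intervention), a normal random intercept per participant, and latent ICCs of 0, 0.3, 0.5 and 0.7.

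**Step 1: population measures.** Difference = 0.40 − 0.20 = 20 points. Risk ratio = 0.40/0.20 = 2.0. Odds ratio = (0.40/0.60)/(0.20/0.80) = 0.6667/0.25 = 2.67.

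**Step 2: conditional odds ratio for the same two proportions.** Given the random intercept, logit P(response) = η + σz with z standard normal, and σ² = [ICC/(1 − ICC)] × π²/3. For ICC 0.5, σ² = 1 × 3.29, so σ = 1.81. The marginal proportion in an arm is the average of expit(η + σz) over z. Solve for η₀ (20%) and η₁ (40%) by Gauss-Hermite quadrature; the conditional odds ratio is exp(η₁ − η₀).

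**Step 3: difference implied if that odds ratio is read as a population one.** Implied intervention rate = (OR × 0.25)/(1 + OR × 0.25), since the control odds are 0.20/0.80 = 0.25. For OR 4.38: 1.095/2.095 = 52.3%, a difference of 32.3 points.

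| Latent ICC | σ | Conditional OR | Implied difference (points) | True difference (points) |
|---|---|---|---|---|
| 0 | 0 | 2.67 | 20 | 20 |
| 0.3 | 1.19 | 3.40 | 26 | 20 |
| 0.5 | 1.81 | 4.38 | 32 | 20 |
| 0.7 | 2.77 | 6.91 | 43 | 20 |

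**Step 4: the reverse direction.** Fix the conditional odds ratio at 3 and ask what difference in proportions it stands for, in points:

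| Control rate | ICC 0 | ICC 0.5 | ICC 0.7 |
|---|---|---|---|
| 5% | 8.6 | 6.0 | 4.4 |
| 15% | 19.6 | 12.3 | 9.1 |
| 30% | 26.2 | 16.6 | 12.5 |

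The same reported odds ratio therefore covers differences from 4.4 to 26.2 points. Even with the control rate known, it does not fix the difference unless the intercept variance is also used.

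**The case against.** The strongest reply is that objective II is in ordinary objective language and need not define a risk-difference estimand. A logistic comparison has the same null hypothesis, gives a valid test, and comes with a 95% interval. Choosing an odds ratio over a difference is a common reporting decision. This stands, and it rules out calling the analysis invalid or saying that the outcome is left unanalysed.

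Other parts of the reply also stand:

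- A reader might infer that the odds ratio overstates the difference in proportions. It cannot, because the two are on different scales. Only a misreading of it as a population odds ratio inflates the implied difference, and the SAP does not present it that way.
- A reader might infer that section 3.1 forbids other measures. It says how estimates will be presented and does not exclude reporting proportions. It simply does not commit to a difference.
- A reader might infer from section 5.3 that the yes/no status will be imputed under a normal model. That section does not say so. Its wording is compatible with imputing continuous ISI and deriving the status.
- The rates and ICCs above are assumptions, and at ICC 0 the gap between the two odds ratios disappears. The participant-level random effect is itself an inference from section 5.1.2.

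The reply does not supply the missing estimate. However objective II is read, the SAP names a difference in proportions and pre-specifies no estimate of it.

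**Conclusion.** The point holds as a mismatch between a stated objective and the planned estimate, in one secondary outcome. The primary analysis of continuous ISI is unaffected, and so is the validity of the test for this outcome.

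That the odds ratio does not determine the difference needs no assumed rates. That it lies further from 1 than the population odds ratio rests on a participant random intercept with variance above zero and a real difference between arms. The size is illustrative only: at assumed rates of 20% and 40%, the conditional odds ratio runs from 2.67 to 6.91 across latent ICCs of 0 to 0.7, for an unchanged difference of 20 points. Zero correlation is unlikely, because each participant's repeated responder status is measured against the same baseline ISI, but the SAP gives nothing from which to fix the actual value.

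**What to change.** - **Section 5.2.1:** keep the mixed logistic model, name its random effect, and label its odds ratio as conditional. Add the marginal proportion in each arm and their difference with a 95% CI, at 3 months first and at 6 weeks and 6 months alongside. Obtain these by averaging model predictions over the covariates in the model and over the random effect. In Stata, the software named in section 5.4, margins does this; state that predictions integrate over the random effect rather than set it to zero.
- **Section 3.1:** add differences in proportions to the listed estimates.
- **Section 5.3:** state that in the imputation sensitivity analysis the 8-point status is derived from imputed continuous ISI.
- **What to avoid:** do not replace the model with unweighted GEE on unimputed data. That generally needs a stronger missingness assumption than the missing-at-random basis in section 5.3, and section 2.4 allows for 30% dropout.

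The cost is a few sentences in the SAP and a post-estimation command. No new data are needed, and the model is unchanged.
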